13 SOURCE DOCUMENTS AND ACCESS TO SOURCE DATA/DOCUMENTS

Study staff will maintain appropriate medical and research records for this study, in compliance with ICH E6, Section 4.9 and regulatory and institutional requirements for the protection of confidentiality of patients. Study staff will permit authorized representatives of the sponsor and regulatory agencies to examine (and when required by applicable law, to copy) research records for the purposes of quality assurance reviews, audits, and evaluation of the study safety, progress and data validity.

14 QUALITY CONTROL AND QUALITY ASSURANCE

To ensure compliance with Good Clinical Practice (GCP) and all applicable regulatory requirements, ITI or its designee may conduct a quality assurance audit of the study site records and regulatory agencies may conduct a regulatory inspection at any time during or after the study. In the event of an audit or inspection, the investigator (and institution) must agree to grant the auditor(s) and inspector(s) direct access to all relevant documents and to allocate their time and the time of their staff to discuss any findings/relevant issues. Responsibility for the accuracy, completeness, and reliability of the study data presented to the sponsor lies with the investigator generating the data.

15 ETHICS/PROTECTION OF HUMAN SUBJECTS

15.1 Ethical Standard

15.2 Independent Ethics Committee or Institutional Review Board

Federal regulations and the International Conference on Harmonisation (ICH) guidelines require that approval be obtained from an Institutional Review Board (IRB) or Independent Ethics Committee (IEC) before participation of human patients in research studies. Before study onset, the protocol, informed consent, advertisements to be used for the recruitment of study patients, and any other written information regarding this study to be provided to the patient or the patient's legal guardian must be approved by the IRB/IEC. Documentation of all IRB/IEC approvals and of the IRB/IEC compliance with ICH harmonised tripartite guideline E6(R1): GCP will be maintained by the study site and will be available for review by the sponsor or its designee.

All IRB/IEC approvals should be signed by the IRB/IEC chairman or designee and must identify the IRB/IEC name and address; the clinical protocol by title, protocol number, or both; and the date approval or a favorable opinion was granted.

The investigator is responsible for providing written summaries of the progress and status of the study at intervals not exceeding 1 year or otherwise specified by the IRB/IEC. The investigator must promptly supply the sponsor or its designee, the IRB/IEC, and, where applicable, the institution, with written reports on any changes significantly affecting the conduct of the study or increasing the risk to patients.

15.3 Ethical Conduct of the Study

The study will be performed in accordance with the ethical principles that have their origin in the Declaration of Helsinki, ICH GCP, and all applicable regulations.

15.4 Institutional Review Board

The protocol, informed consent form(s), recruitment materials, and all patient materials will be submitted to the IRB/IEC and local regulatory authorities (where applicable) for review and approval. Approval of both the protocol and the consent form must be obtained before any patient is enrolled. Any amendment to the protocol will require review and approval by the IRB/IEC as well as local regulatory authorities, before the changes are implemented in the study.

15.5 Informed Consent Process

15.6 Patient Information and Consent

Informed consent is a process that is initiated prior to the individual agreeing to participate in the study and continues throughout study participation. Extensive discussion of risks and possible benefits of study participation will be provided to patients and their families, if applicable. A consent form describing in detail the study procedures and risks will be given to the patient. Consent forms will be IRB/IEC-approved, and the patient is required to read and review the document or have the document read to him or her. The investigator or designee will explain the research study to the patient and answer any questions that may arise. The patient will sign the informed consent document prior to any study-related assessments or procedures. Patients will be given the opportunity to discuss the study with their surrogates or think about it prior to agreeing to participate. They may withdraw consent at any time throughout the course of the study. A copy of the signed informed consent document will be given to their records. The rights and welfare of the patients will be protected by emphasizing to them that the quality of their clinical care will not be adversely affected if they decline to participate in this study.

The consent process will be documented in the clinical or research record.

A written informed consent in compliance with US Title 21 Code of Federal Regulations (CFR) Part 50 shall be obtained from each patient before entering the study or performing any unusual or nonroutine procedure that involves risk to the patient. An informed consent template may be provided by the sponsor to clinical study sites. If any institution-specific modifications to study-related procedures are proposed or made by the study site, the consent should be reviewed by the sponsor, its designee, or both before IRB/IEC submission. Once reviewed, the consent will be submitted by the investigator to his or her IRB/IEC for review and approval before the start of the study. If the ICF is revised during the course of the study, all active participating patients must sign the revised form.

Before recruitment and enrollment, each prospective patient or his or her legal guardian will be given a full explanation of the study and be allowed to read the approved ICF. Once the investigator is assured that the patient/legal guardian understands the implications of participating in the study, the patient/legal guardian will be asked to give consent to participate in the study by signing the ICF.

The investigator shall retain the signed original ICF(s) and give a copy of the signed original form to the patient or legal guardian.

Neither the sponsor nor the CRO is financially responsible for further testing or treatment of any medical condition that may be detected during the screening process. In addition, in the absence of specific arrangements, neither the sponsor nor the CRO is financially responsible for further treatment of the patient's disease.

15.7 Patient Confidentiality

All laboratory specimens, evaluation forms, reports, and other records will be identified in a manner designed to maintain patient confidentiality. All records will be kept in a secure storage area with limited access. Clinical information will not be released without the written permission of the patient (or the patient's legal guardian), except as necessary for monitoring and auditing by the sponsor, its designee, the US FDA or other local regulatory authorities, or the IRB/IEC.

The investigator and all employees and coworkers involved with this study may not disclose or use for any purpose other than performance of the study any data, record, or other unpublished, confidential information disclosed to those individuals for the purpose of the study. Prior written agreement from the sponsor or its designee must be obtained for the disclosure of any said confidential information to other parties.

15.8 Future Use of Stored Specimens and Other Identifiable Data

Residual blood samples collected for pharmacokinetic analysis may be maintained after the study is complete. Patients will provide informed consent form for the future use of his/her samples. The sponsor or designee will maintain the samples up to 10 years following the completion of the study for pharmacokinetic analysis purposes only. Confidentiality will be protected for any future studies with the stored samples or data de-identified (identified by patient identification number only). Genetic testing will not be performed.

16 DATA HANDLING AND RECORD KEEPING

Prior to beginning the study, the investigator will be asked to comply with ICH E6(R1) 8.2 and Title 21 of the US Code of Federal Regulations (CFR) by providing the following essential documents, including but not limited to:

- IRB/IEC approval
- Original investigator-signed investigator agreement page of the protocol
- Form FDA 1572, fully executed, and all updates on a new fully executed Form FDA 1572
- Curriculum vitae for the investigator and each subinvestigator listed on Form FDA 1572
- Financial disclosure information to allow the sponsor to submit complete and accurate certification or disclosure statements required under 21 CFR 54. In addition, the investigators must provide to the sponsor a commitment to promptly update this information if any relevant changes occur during the course of the investigation and for 1 year after study completion.
- IRB/IEC-approved informed consent, samples of site advertisements for recruitment for this study, and any other written information regarding this study that is to be provided to the patient or legal guardian, and
- Laboratory certifications and normal ranges for any local laboratories used by the study site, in accordance with 42 CFR 493

As part of the responsibilities assumed by participating in the study, the investigator agrees to maintain adequate case histories for the patients treated as part of the research under this protocol. The investigator agrees to maintain accurate eCRFs and source documentation as part of the case histories. These source documents may include records of screening assessments such as the M.I.N.I., laboratory reports, and ECG strips.

After database lock, each study site will receive a CD-ROM containing all of their study site-specific eCRF data as entered into the EDC, including full discrepancy and audit history. Additionally, a CD-ROM copy of all of the study site's data will be created and sent to the sponsor for storage. The CRO will maintain a duplicate CD-ROM copy for their records. In all cases, patient initials will not be collected or transmitted to the sponsor.

16.1 Data Management Responsibilities

Clinical data management will be performed in accordance with applicable ITI standards and data cleaning procedures to ensure the integrity of the data, e.g., removing errors and inconsistencies in the data. Adverse events and concomitant medication terms will be coded using MedDRA, an internal validated medication dictionary.

16.2 Data Capture Methods

Clinical study site personnel will enter patient data into electronic data capture (EDC). All eCRF fields are to be filled in. If an item is not available or is not applicable, this fact should be indicated. Blank fields should not be present unless otherwise directed. The analysis data sets will be a combination of these data and data from other sources (e.g., laboratory data).

16.3 Types of Data

Types of data that will be collected includes efficacy outcome assessments, safety outcome assessments, and pharmacokinetic assessments.

16.4 Schedule and Content of Reports

The sponsor or designee will be responsible for clinical monitoring plans and reports, safety monitoring plans, data management plans, statistical analysis plans and the clinical study report. Masking procedures and breaking the blind are described in Sections 5.4.2 and 5.4.3, respectively.

16.5 Study Records Retention

Essential documents should be retained until at least 2 years after the last approval of a marketing application in an ICH region and until there are no pending or contemplated marketing applications in an ICH region or at least 2 years have elapsed since the formal discontinuation of clinical development of the investigational product. These documents should be retained for a longer period, however, if required by the applicable regulatory requirements or by an agreement with the sponsor. It is the responsibility of the sponsor to inform the investigator/institution as to when these documents no longer need to be retained.

16.6 Protocol Deviations

The investigator or designee must document and explain in the patient's source documentation any deviation from the approved protocol. The investigator may implement a deviation from, or a change of, the protocol to eliminate an immediate hazard to study patients without prior IRB/IEC approval. As soon as possible after such an occurrence, the implemented deviation or change, the reasons for it, and any proposed protocol amendments should be submitted to the IRB/IEC for review and approval, to the sponsor for agreement, and to the regulatory authorities, if required.

A deviation from the protocol is an unintended or unanticipated departure from the procedures or processes approved by the sponsor and the IRB/IEC and agreed to by the investigator. A significant deviation occurs when there is nonadherence to the protocol by the patient or investigator that results in a significant, additional risk to the patient. Significant deviations can include nonadherence to inclusion or exclusion criteria, enrollment of the patient without prior sponsor approval, or nonadherence to FDA or local regulatory authority regulations or ICH GCP guidelines, and will lead to the patient being withdrawn from the study (Section 5.5).

Protocol deviations will be documented by the clinical monitor throughout the course of monitoring visits. Principal investigators will be notified in writing by the monitor of deviations. The IRB/IEC should be notified of all protocol deviations in a timely manner.

1. LIST OF ABBREVIATIONS

| AE | Adverse Event |
|----------|---|
| AIMS | Abnormal Involuntary Movement Scale |
| ALT | Alanine aminotransferase |
| ANCOVA | Analysis of Covariance |
| AR(1) | Autoregressive(1) |
| ARH(1) | Heterogeneous autoregressive(1) |
| AST | Aspartate aminotransferase |
| BARS | Barnes Akathisia Rating Scale |
| BLQ | Below limit of quantification |
| BMI | Body mass index |
| C-SSRS | Columbia – Suicide Severity Rating Scale |
| CGI-BP-S | Clinical Global Impression Scale – Bipolar version, Severity |
| CI | Confidence interval |
| CPK | Creatine phosphokinase |
| CS | Compound symmetry |
| CSH | Heterogeneous compound symmetry |
| DNA | Deoxyribonucleic acid |
| ECG | Electrocardiogram |
| eCRF | Electronic Case Report Form |
| ENR | All Subjects Enrolled |
| FA0(q) | No Diagonal Factor Analytic |
| GGT | Gamma-glutamyl transferase |
| HbA1c | Glycated Hemaglobin A1c |
| HDL | High-density lipoprotein |
| HIV | Human Immunodeficiency Virus |
| HR | Heart rate |
| IEC | Independent Ethics Committee |
| IRB | Institutional Review Board |
| ITCI | Intra-Cellular Therapies, Inc. (Sponsor) |
| ITT | Intent-to-treat |
| LDL | Low-density lipoprotein |
| LOCF | Last observation carried forward |
| LOE | Lack of efficacy |
| LSM | Least-squares Mean |
| MADRS | Montgomery-Åsberg Depression Rating Scale |
| MAR | Missing at random |
| MCMC | Monte Carlo Markov Chain |
| MedDRA | Medical Dictionary for Regulatory Activities |
| MI | Multiple imputation |
| MMRM | Mixed-Effects Model for Repeated Measures |
| MNAR | Missing not at random |
| PK | Pharmacokinetic(s) |
| PP | Per protocol |
| PR | PR interval of the electrocardiogram; time duration between the P and |

Document: Author:

...\ITI\ITI-007\MYA11638\Biostatistics\Documentation\SAP\ITI-007-404 SAP Final V1.0 12JUN2019.docx

Version Number:1.0

STATISTICAL ANALYSIS PLAN: PROTOCOL ITI-007-404
Page 8 of 53

| | R waves |
|----------|--|
| PT | Preferred Term |
| Q-LES-Q- | Quality of Life Enjoyment and Satisfaction Questionnaire – Short |
| SF | Form |
| QRS | QRS interval of the electrocardiogram; duration of the QRS complex |
| QT | QT interval of ECG, duration between the Q and T waves |
| QTc | QT interval of ECG corrected for heart rate |
| QTcB | QT interval of ECG corrected for heart rate using Bazett's formula |
| QTcF | QT interval of ECG corrected for heart rate using Fridericia's formula |
| RNA | Ribonucleic acid |
| RND | All Subjects Randomized |
| RR | Time duration between two consecutive R waves of the |
| | electrocardiogram |
| SAE | Serious Adverse Event |
| SAF | Safety Analysis |
| SAP | Statistical Analysis Plan |
| SAS | Simpson-Angus Scale |
| SAS® | Statistical Analysis Software |
| SENS | Sensitivity |
| SD | Standard deviation |
| SMQ | Standardized MedDRA Queries |
| SOC | System Organ Class |
| SUPPP | Supportive Per Protocol |
| TEAE | Treatment-emergent adverse event |
| TLFs | Tables, Listings and Figures |
| TOEP | Toeplitz structure |
| TOEPH | Heterogeneous Toeplitz structure |
| ULQ | Upper limit of quantification |
| WBC | White blood cells |
| WHO | World Health Organisation |
| YMRS | Young Mania Rating Scale |

Document: ...\ITI\ITI-007\MYA11638\Biostatistics\Documentation\SAP\ITI-007-404 SAP Final V1.0 12JUN2019.docx

Author: Version Number:1.0

Page 9 of 53

2. Introduction

This document describes the rules and conventions to be used in the presentation and analysis of efficacy, safety, and pharmacokinetic (PK) data for Protocol ITI-007-404. It describes the data to be summarized and analyzed, including specifics of the statistical analyses to be performed.

This statistical analysis plan (SAP) is based on Protocol Version 1.3, dated November 5, 2018.

3. STUDY OBJECTIVES

[figure not shown]
3.1. PRIMARY OBJECTIVE

The primary objective of this study is to compare the efficacy of lumateperone administered orally once daily to that of placebo as measured by mean change from baseline to Day 43 in the total score on the Montgomery-Åsberg Depression Rating Scale (MADRS) in subjects with Bipolar Depression.

3.2. SECONDARY OBJECTIVES

[figure not shown]
3.2.1. KEY SECONDARY OBJECTIVE

The key secondary objective of this study is to compare the efficacy of lumateperone administered orally once daily to that of placebo as measured by mean change from baseline to Day 43 in the total score on the Clinical Global Impression Scale, Bipolar version – Severity (CGI-BP-S) in subjects with Bipolar Depression.

Document: Author: Version Number 1.0

3.2.3. SAFETY SECONDARY OBJECTIVES

The safety secondary objectives of this study are to determine the safety and tolerability of lumateperone, administered orally once daily for 6 weeks in subjects with Bipolar Depression, compared to placebo. Safety and tolerability will be assessed in relation to:

- Incidence of adverse events (AEs);
- Mean change from baseline in the Young Mania Rating Scale (YMRS);
- Mean change from baseline in the Columbia Suicide Severity Rating Scale (C-SSRS);
- Mean change from baseline in the Abnormal Involuntary Movement Scale (AIMS);
- Mean change from baseline in the Barnes Akathisia Rating Scale (BARS);
- Mean change from baseline in the Simpson Angus Scale (SAS);
- Changes from baseline in clinical laboratory evaluations;
- Changes from baseline in electrocardiograms (ECGs);
- Changes from baseline in vital sign measurements;
- Physical and neurological examination findings.

Document: Author:

4. STUDY DESIGN

4.1. GENERAL DESCRIPTION

Study participation will last approximately 10 weeks (up to 9 visits) and will include the following three periods: a Screening Period, lasting up to 2 weeks, unless the Sponsor or representative, in extenuating circumstances related to the subject or the caregiver, where applicable, authorizes a longer period; a 6-week double-blind On-Treatment Period of daily administration of the study medication; and a Safety Follow-up Period of approximately 2 weeks after the last dose of study medication for subjects who completed the planned 6 weeks of treatment. The timing of assessments during each study period are described in the Schedule of Events (Appendix A of the protocol and Appendix 1).

5. FINAL AND INTERIM ANALYSES

5.1. BLINDED SAMPLE SIZE RE-ESTIMATION

An unplanned blinded sample size re-estimation was conducted based on a blinded data review of the efficacy data during the study. The estimated pooled standard deviation (SD) was 8.82, which was larger than what was assumed at study planning. The sample size was therefore increased to a total of 350 randomized subjects, based on an assumed SD of 9.0, to ensure 90% statistical power.

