All safety parameters will be summarized using the Safety Analysis Set. Safety data such as reported and observed AEs, treatment emergent adverse events (TEAEs) and SAEs, clinical laboratory results, vital signs, physical and neurological examination findings, ECGs, and the different rating scales (YMRS, C SSRS, AIMS, BARS, and SAS) will be summarized by treatment group and visit. When appropriate, out of range values will be flagged in data listings and tabulated. Shift tables will be prepared for pre-specified safety measures, such as laboratory parameters, ECG and weight.

Sample Size:

Approximately 350 patients will be randomly assigned in a 1:1 ratio to 1 of the 2 treatment groups (ITI-007 60 mg or placebo). A sample size of 350 randomized patients will provide approximately 326 evaluable patients assuming a 10% early discontinuation rate before the first post-dose assessment of the primary efficacy outcome measure (MADRS). Approximately 163 patients per treatment group will provide 85% power to detect a clinically relevant treatment difference from placebo of 3 points on the MADRS total score with a common standard deviation of 9.0 at an overall 2-sided significance level of 0.05.

Schematic of Study Design:

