12.1 Sample Size Considerations

Approximately 350 patients will be randomly assigned in a 1:1 ratio to 1 of the 2 treatment arms (60 mg ITI-07 or placebo). A sample size of 350 patients randomized, which will provide approximately 326 evaluable patients (approximately 163/treatment group) assuming a 10% early discontinuation rate before the first post-dose assessment in the primary efficacy outcome measure (MADRS), will provide 85% power to detect a clinically relevant treatment difference from placebo of 3 points on the MADRS total score with ITI-007, with a common standard deviation of 9.0at an overall 2-sided significance level of 0.05.

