All investigative sites with fewer than 4 ITT subjects will be pooled as follows: The largest site with fewer than 4 ITT subjects will be pooled with the smallest site with fewer than 4 ITT subjects. If this results in a pooled site still having fewer than 4 ITT subjects, this site will be pooled together with the next smallest investigative site, if one exists; otherwise, no further pooling is needed. Sites with the same number of ITT subjects will be ordered in ascending order of their numerical site identification number. This will serve as a tie-breaker rule in case multiple sites have the same number of ITT subjects. If the primary efficacy analysis model, described in section 15.1.3 presents convergence issues due to the too small number of subjects per site, the same site pooling algorithm will be applied again, but this time pooling sites with fewer than 8 ITT subjects. Should the primary efficacy analysis model still present convergence issues, after testing the sequence of correlation structures listed in section 15.1.3, then including the site effect in the model will be reconsidered and may be dropped. These pooled investigative sites, as determined based on the primary efficacy response variable, will be used for any analysis that has investigative site as a fixed effect in the model. The actual investigative site numbers will be included in the by-subject listings.

The default significance level for statistical tests will be 5%; confidence intervals (CIs) will be 95% and all tests will be two-sided, unless otherwise specified in the description of the analyses. All analyses will be conducted using SAS® version 9.4 or higher.

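### The SAP claims 90% power for 350 randomized patients at SD 9.0; the protocol's 85% is the figure that reproduces, and its 10% loss leaves 315 evaluable patients (about 84% power), not 326

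*SAP*

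**What the plan says.** SAP section 5.1 says that a blinded review gave a pooled SD of 8.82, larger than had been assumed at planning, and that the sample size was therefore "increased to a total of 350 randomized subjects, based on an assumed SD of 9.0, to ensure 90% statistical power". It gives no effect size, significance level or loss rate for this calculation.

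Protocol section 12.1 starts from the same 350 randomized patients, 1:1, "which will provide approximately 326 evaluable patients (approximately 163/treatment group) assuming a 10% early discontinuation rate"; losses are counted up to the first MADRS after dosing. It says this number "will provide 85% power to detect a clinically relevant treatment difference from placebo of 3 points on the MADRS total score". The SD used there is again 9.0, and the test is two-sided at 0.05. The Protocol Summary repeats the count: "A sample size of 350 randomized patients will provide approximately 326 evaluable patients assuming a 10% early discontinuation rate". It also repeats the 85% power.

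**The concern.** Two planning figures look wrong.

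- **Power.** The two documents attach different power (90% and 85%) to the same randomized number and the same SD. At most one can be right.
- **Evaluable count.** The protocol's 326 does not follow from the loss rate given in the same sentence.

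Section 5.1 is the account the SAP gives of an unplanned change to the sample size during the study, and 90% power is the reason it offers. If the design does not deliver 90%, the stated purpose of the change was not met. A non-significant result would then be read against a type II error of 10% when the planning inputs imply about 15–16%, which overstates the evidence against a 3-point effect.

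**Working it through.** **Inputs**

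| Input | Value | Source |
|---|---|---|
| Difference δ | 3 MADRS points | Protocol 12.1 and Summary (the SAP gives none) |
| SD σ | 9.0 | Protocol 12.1, Summary, SAP 5.1 |
| Blinded pooled SD | 8.82 | SAP 5.1 |
| Test level | 0.05, two-sided | Protocol 12.1; SAP section 7 default |
| Randomized | 350, 1:1 (175 per arm) | Protocol 12.1 |
| Evaluable | 326 (163 per arm) | Protocol 12.1 |
| Loss before first post-dose MADRS | 10% | Protocol 12.1 |

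**Formula.** For a two-sample comparison of means with n per arm, SE = σ√(2/n) and power ≈ Φ(δ/SE − 1.96). The noncentral t version is shown beside the normal approximation.

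**Step 1: the protocol's 85%.** With n = 163, SE = 9√(2/163) = 0.997 and 3/0.997 = 3.009. Power = Φ(3.009 − 1.960) = Φ(1.049) = 85.3% (t: 85.1%). The protocol's figure reproduces from its own 163 per arm.

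**Step 2: the SAP's 90%.**

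| n per arm | Meaning | SD 9.0, normal | SD 9.0, t | SD 8.82, t |
|---|---|---|---|---|
| 157.5 | true 10% loss | 84.1% | 83.9% | 85.3% |
| 163 | evaluable number as stated | 85.3% | 85.1% | 86.5% |
| 175 | nobody lost | 87.7% | 87.5% | 88.7% |

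No row reaches 90%, even with no loss and the smaller observed SD.

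**Step 3: what 90% would need at SD 9.0.** n = 2σ²(1.960 + 1.282)²/δ² = 18 × 10.507 = 189.1, so 190 per arm. By the t distribution 190 gives 89.99%, so 191 are needed. That is 382 evaluable, and 382/0.9 = 424.4, so 425 randomized with 10% loss (423 by the normal formula: 380/0.9 = 422.2). Put the other way, the difference detectable with 90% power is 3.24 points at 163 per arm and 3.13 points at 175 per arm.

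**Step 4: the evaluable count.** 350 × 0.90 = 315, which is 11 fewer than 326. Since 326/350 = 0.931, the implied loss is 6.9%; a 7% loss gives 350 × 0.93 = 325.5. To keep 326 evaluable with 10% loss needs 326/0.9 = 362.2, so 363 randomized.

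**The case against.** The strongest reply is that these are powers for a simple two-sample comparison, whereas the primary analysis is an MMRM with baseline MADRS as a covariate. The documents do not say whether 9.0 is the SD of the raw change score or a residual SD after adjustment. If it is the raw SD, adjustment could raise power. By the normal formula, 90% needs a residual SD of 8.66 at 175 per arm, 8.36 at 163 and 8.21 at 157.5. Taking residual SD = 9√(1 − ρ²), this means a correlation ρ between baseline and change of about 0.27, 0.37 and 0.41 respectively. These correlations are assumptions; neither document gives one. Dropout after the first assessment would pull power the other way and is not quantified either. This stands as a limit on what the 84% means. It does not rescue the 90%, because the protocol's 85% comes from the unadjusted calculation on the same 350 patients and SD.

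Second, SAP 5.1 states no effect size, so the comparison borrows the 3 points from the protocol. That is correct, and the conclusion is conditional on it. But 3 points is the only difference given in either document. A one-sided 0.05 test would give 91.4% at 163 per arm, but both documents specify two-sided tests.

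Third, the two slips are unequal. Moving from 326 to 315 evaluable costs only about 1 point of power (85.1% to 83.9%), and the protocol calls its counts approximate. This is accepted: the 90% is the material error. Still, an 11-patient gap is more than rounding when the loss rate is stated alongside it.

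Finally, power enters no planned analysis and type I error is unaffected. That is true, and it is why the correction is cheap; it does not make the stated power right.

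**Conclusion.** The concern holds. For a 3-point difference, SD 9.0 and a two-sided 0.05 test, 350 randomized patients give 83.9% power after the stated 10% loss, 85.1% with the stated 326 evaluable, and 87.5% with no loss at all. The SAP's 90% is not attainable at its own sample size and SD unless the target difference exceeds 3 points (about 3.13 with no loss, 3.24 at 163 per arm). The protocol's 85% is sound for 163 per arm, but 163 per arm corresponds to a loss of 6.9%, not 10%.

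These are powers at the documents' planning inputs. They rest on the protocol's 3 points also being the re-estimation target, and they make no allowance for covariate adjustment or later dropout.

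**What to change.** - **SAP 5.1:** replace the 90% with the power the design delivers, and state the effect size, significance level and loss rate so that the figure can be reproduced.
- **Protocol 12.1 and Summary:** choose one consistent set. Either keep the 10% loss and give 315 evaluable (about 157 per arm) with about 84% power, or keep 326 evaluable and 85% and restate the loss as about 7%.
- **Both documents:** use the same figures throughout.

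Correcting the record needs no extra patients and no change to the model, analysis sets or alpha. The cost is a wording change in each document and a less favourable stated power. If 90% was the real target of the re-estimation, rewording cannot supply it: at these inputs it would take about 425 randomized with 10% loss, and the sponsor should say which power was intended.
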